## **9 STATISTICAL CONSIDERATIONS**

### **9.1 General Design Issues**

The primary purpose of this pilot is to assess feasibility of collecting the primary clinical outcome, defined as emergency department visits among the PWD. Secondary outcomes will assess the feasibility of implementation, number of contacts between nurse care managers and care partners, and documented advance care planning.

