### **9.3 Outcomes**

The primary outcome for the is pilot is emergency room visits within 6 months. We will rely on Epic and Medicare claims data for all measures of healthcare service utilization and costs, care intensity / quality, documentation of advance care planning, and documentation of medication review. These outcomes will be assessed for all PWD who are cared for by selected nurse care managers using retrospective analysis of existing health care data. We anticipate that this will include 150 PWD among care managers who receive early training and 150 PWD who receive delayed training. These data are housed in an existing data repository; we anticipate minimal missing data. Key secondary outcomes will assess the number of contacts between nurse care managers and care partners, and documented advance care planning; these measures likewise available from the existing data warehouse and we anticipate minimal missing data.

In order to ensure systematic capture of key clinical outcomes within this pilot, we will survey caregivers of PWD receiving care management from the 30 selected nurse care managers and meeting our inclusion and exclusion criteria at months 3 and 9. We expect that a minimum of 50% of caregivers will complete each survey, yielding an expected sample of 75 PWD caregiver respondents completing each survey and 37 PWD caregiver respondents completing both an initial and follow- up survey for nurses assigned to the early and the delayed training. We will assess the completeness and correlation of behavioral symptoms of dementia, caregiver depression, caregiver burden, and PWD quality of life captured via trained nurse care managers (and documented in Epic or iCMP data) with caregiver survey responses.

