2.3 Secondary outcome measure

The secondary outcome is the change in caregiver distress between baseline and 6-month follow-up survey. Caregiver distress is measured by the Neuropsychiatric Inventory Questionnaire (NPI-Q), a brief proxy/caregiver-report of patient severity and caregiver distress across 12 neuropsychiatric symptom domains. Scores on the NPI-Q Distress scale can range from 0 to 60. The NPI-Q has demonstrated reliability and validity in dementia patients.

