6 SAMPLE SIZE

Preliminary estimates based on 2018 data suggested that on average FTE iCMP nurse care managers in our health system have 10 Medicare beneficiaries diagnosed with dementia on their panels. For this pragmatic quality improvement trial, we planned to engage 30 active iCMP nurse care managers (out of a total of approximately 65 nurse care managers) serving approximately 300 PWD and their caregivers (150 in each arm).

Among the 30 nurse care managers actually selected for the study, a total of 393 PWD met the inclusion criteria, 206 patients corresponding to the 15 intervention nurses and 187 patients corresponding to the 15 control nurses. The population was refined to exclude patients without a designated caregiver, deceased or moved to skilled nursing facility (for full list of exclusions see Figure 1 of cohort flowchart). This validated cohort included 143 PWD in the intervention group, and 113 PWD Controls.

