7.1.2 Clinical Outcome Cohort

For the NPI-Q Distress outcome measurement, the validated cohort was restricted to baseline and follow-up survey respondents with completed NPI-Q Distress measures (Intervention n=35, Control n=28). (See Figure 1 of cohort flowchart)

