8.2 Secondary outcome analysis

The secondary outcome of change in NPI-Q distress score from baseline survey to 6-month follow-up survey for intervention and control cohorts is compared using a difference-in-differences model with a linear distribution and identity link. Models adjusted for differences in demographic characteristics (race, ethnicity, age) and PHQ-8 at baseline. A point difference of 2 or greater on the NIPQ-Distress scale is generally considered to be clinically meaningful; therefore a difference in differences estimate of 2 or more in this model (i.e., a relative difference of 2 points or more between Intervention and Controls) would suggest a meaningful impact of the Intervention.

We hypothesized a relative decrease in NPI-Q distress in the Intervention group as compared to Controls.

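### The SAP omits the protocol's two named key secondary outcomes, nurse contacts and documented advance care planning, without explanation, and makes NPI-Q Distress (63 complete pairs) the only secondary outcome

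*SAP*

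**What the plan says.** Protocol 9.3 states: "Key secondary outcomes will assess the number of contacts between nurse care managers and care partners, and documented advance care planning". The same sentence adds "these measures likewise available from the existing data warehouse and we anticipate minimal missing data". Protocol 9.1 agrees: "Secondary outcomes will assess the feasibility of implementation, number of contacts between nurse care managers and care partners, and documented advance care planning". The measures table in protocol section 6 also labels advance care planning documentation and patient contacts (under care intensity) as secondary.

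SAP 2.3 speaks in the singular: "The secondary outcome is the change in caregiver distress between baseline and 6-month follow-up survey", measured by the NPI-Q Distress scale. SAP 8.2 specifies one model, for "The secondary outcome of change in NPI-Q distress score from baseline survey to 6-month follow-up survey". SAP 7.1.2 says the population for it is "restricted to baseline and follow-up survey respondents with completed NPI-Q Distress measures", which is 35 in the intervention group and 28 controls. SAP 7.3 rules out imputation.

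The SAP gives no definition, analysis population or model for contacts or advance care planning. Advance care planning appears only in its introduction. No reason for the difference is given.

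**The concern.** The two documents disagree on what the secondary outcomes are, and an analyst who follows the SAP will never analyse the two that the protocol calls key. Three things are at stake.

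- **Relevance.** Contacts and advance care planning are the measures closest to what training nurses would change. Protocol 9.4 also plans to examine process measures as mediators, which cannot be done if they are left out.
- **Coverage.** Outcomes expected to be nearly complete in routine data give way to one that exists only for caregivers who answered two surveys.
- **Interpretation.** The protocol gives NPI-Q Distress no priority over PHQ-8, caregiver burden, QOL-AD or unmet need. In the SAP, PHQ-8 survives only as a baseline characteristic and adjustment covariate. If one subscale is reported alone, a reader cannot rule out selective reporting.

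**Working it through.** **1. Reproduce the protocol's survey figure.** Protocol 9.3 assumes 150 PWD per arm and at least 50% response at each survey. Expected pairs per arm = 150 × 0.50 × 0.50 = 37.5, stated as 37. Two arms give 2 × 37 = 74.

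**2. Compare with what was obtained.** SAP 7.1.2 gives 35 + 28 = 63 pairs, and 63/74 = 85% of plan. The survey came close to its own target.

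**3. Share of the cohort.** SAP section 6: "This validated cohort included 143 PWD in the intervention group, and 113 PWD Controls", so 143 + 113 = 256.

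- Overall: 63/256 = 24.6%
- Intervention: 35/143 = 24.5%
- Control: 28/113 = 24.8%

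The documents give no count of PWD with usable contact or advance care planning data. Taking 256 as the sample for those outcomes is therefore an upper bound, resting on the protocol's expectation of minimal missing data.

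**4. What the sample sizes mean for precision (illustrative).** The SAP gives no power calculation for the secondary outcome. Assume two-sided alpha 0.05, 80% power and no clustering. The detectable difference in SD units is (1.960 + 0.842) × √(1/n₁ + 1/n₂):

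- 35 vs 28: 2.802 × √(1/35 + 1/28) = 0.71 SD
- 143 vs 113: 2.802 × √(1/143 + 1/113) = 0.35 SD

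With 30 nurses, the mean cluster size m is 63/30 = 2.1 or 256/30 = 8.5. Multiplying by √(1 + (m − 1) × ICC) for an assumed ICC of 0.01 to 0.10 gives 0.71 to 0.75 SD and 0.37 to 0.47 SD respectively. Clustering narrows the gap but does not close it. The SD scale is only a common yardstick here, since contacts are counts and advance care planning is binary.

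**5. A limit on that advantage.** Protocol 9.4 adjusts for dementia stage and severity. The measures table takes this from the caregiver survey only. At the planned 50% response, a complete-case model with that covariate would keep about 0.50 × 256 = 128 PWD. The larger sample is available only if adjustment is confined to Epic and claims covariates.

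**6. Timing.** SAP 7.1.2 reports how many respondents completed NPI-Q Distress at both surveys, SAP 7.2 reports which baseline variables differed between arms, and SAP section 9 reports that no adverse events occurred. Follow-up survey data had therefore been collected when this text was written. Neither document dates the choice of NPI-Q Distress.

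**The case against.** The best defence is that NPI-Q is not new. The protocol's measures table labels it both primary and secondary, a higher label than the plain secondary given to contacts and advance care planning. The survey battery in protocol 6.2.2 notes that it covers caregiver distress, and behavioral symptoms and caregiver burden are in the Précis's secondary objective. The protocol's own hierarchy is also not uniform across the Précis, the measures table and section 9. In addition, this is a feasibility pilot with no stated power target. All of this stands, and it limits how the point may be described.

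A reader might go further and infer:

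- **That the SAP swapped in an unplanned outcome.** The documents do not support this: the instrument and its distress component were planned.
- **That the SAP's choice suffered from a failed survey.** It did not: 63 of about 74 planned pairs were obtained.
- **That the subscale was picked because its result was favourable.** Realised cohort sizes and baseline imbalances show that data were in hand. They do not show that outcome results guided the choice.
- **That all 393 PWD who met the inclusion criteria could supply the omitted outcomes.** That count precedes the removal of patients with no designated caregiver, for whom contact with a care partner cannot be measured. It also precedes the removal of those who had died or moved to a skilled nursing facility.

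None of this explains why two outcomes that section 9 of the protocol names as key have no analysis in the SAP.

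**Conclusion.** The discrepancy is real and should be corrected. The SAP omits both outcomes that protocol 9.3 names as key secondary, without explanation. It promotes one planned survey subscale, observed in 63 complete pairs (24.6% of 256), to the only secondary outcome. The accurate description is promotion plus omission. On timing, the documents show neither that the choice preceded the data nor that results drove it.

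The finding rests on setting the two texts side by side and needs no sample-size assumption. The precision comparison (about 0.71 SD against 0.35 SD without clustering) is illustrative: it assumes alpha, power and near-complete warehouse data for the 256. The primary objective, the feasibility of collecting ED visit data, is not affected.

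**What to change.** In SAP 2.3 and 8.2:

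1. **Restore both outcomes in the validated cohort**, with arm as predictor and a nurse random effect, as in protocol 9.4. For contacts over the 6-month window between early and delayed training, use a negative binomial model, adding log follow-up time as an offset (9.4 does not mention one). For advance care planning documented in that window, use a logistic model.
2. **Adjust only for covariates held in Epic or claims**, for example age, race, ethnicity and Elixhauser score. State that dementia stage is left out because it comes only from the survey and would restrict the sample to respondents.
3. **Choose one definition of contacts.** Protocol 9.3 refers to care partners, the measures table to patients, and the program-data paragraph of section 6 to either patient or caregiver.
4. **Report NPI-Q Distress beside** NPI-Q Severity, PHQ-8, caregiver burden, QOL-AD and unmet need. State that it was singled out after the protocol, with the date and the reason.

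The cost is SAP wording, two extra models on data that the protocol says are already in the warehouse, some work to settle the contacts definition, and a longer list of secondary results to present and interpret with restraint.

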### Objectives

Our primary objective is to test the feasibility of collecting emergency department visit data among the PLWD cared for by the primary care practices.

Our secondary objective is to determine the short-term impacts of an adapted Care Ecosystem curriculum and workflow on care management processes, healthcare utilization, behavioral symptoms of dementia, caregiver burden, and caregiver depression.

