As noted in the background, PWD receiving CareEco had improved quality of life and reduced emergency department visits. Caregivers experienced decreased depression and caregiver burden within the first 6 months. The evidence from the CareEco trial, therefore, supports a pragmatic trial as a next step. Since the conclusion of the CareEco study, an academic health system in Colorado, an integrated health system in Minnesota, and an academic integrated health system in New Orleans have all adopted CareEco as a care delivery model. They used the Open-access CareEco tools (toolkit, educational materials, data dictionary) to develop projects at each of their sites, demonstrating that it is feasible to adapt and implement CareEco in diverse settings. While CareEco has been adopted by 3 other health systems, none of these systems are formally evaluating its implementation in an embedded trial. In the original clinical trial, the intervention posed minimal risk, with no indication of adverse events or unintended consequences.

Under value-based contracts, care management programs, and in particular care management embedded within primary care practices, have become a common strategy to address inappropriate utilization among complex patients. We propose to build on this model and test an adaptation of Care Eco that involves uptraining existing primary care embedded nurse care managers rather than adding a new care navigator to address the needs of PWD and their caregivers. This adaption both improves the fit with our health system and would be applicable to many other accountable care organizations with existing high-risk care management programs. We anticipate that this adaptation will enhance scalability by using pre-existing staffing infrastructure, improve efficiency by weaving dementia care into an established care delivery model, and optimize sustainability by matching evidence-based workflow protocols with engaged clinicians (iCMP nurse care managers).

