2.2 Primary outcome measure

The primary outcome is the change in ED visits per member per month from the 12 months prior the adapted Care Ecosystem training to the 6 months post training.

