7.2 General considerations for statistical analysis

Data are summarized by treatment group. Continuous variables are summarized using mean and standard deviations. Categorical variables are summarized using frequency and percentages. SAS Enterprise Guide 7.1 is used for analyses.

Demographic and other baseline characteristics are compared between groups. Race, ethnicity, age, gender, language, marital status, baseline primary care provider (PCP) utilization per member per month (PMPM), baseline inpatient utilization PMPM, baseline ED utilization PMPM, and baseline observation visits PMPM are summarized for the Utilization Outcome Cohort. For the Clinical Outcome Cohort, the same characteristics will be summarized, as well as NPI-Q Distress (caregiver distress), NPI-Q Severity (patient symptom severity), PHQ-8 (caregiver depression), and Quick Dementia Rating Scale (patient dementia severity) from the baseline survey.

A combination of t-tests (at $p < .05$), chi square tests (at $p < .05$) and standardized mean differences (cutoff of .15 or greater) were used to identify differences between cohorts and covariates for risk adjusted models. Based on these criteria, race, ethnicity, and age were identified as different between intervention and control in the Utilization Outcome Cohort, as were baseline PCP visits, inpatient hospitalizations, and Observation visits. For the Clinical Outcome Cohort, PHQ-8 (caregiver depression) was different across Intervention and Control. Risk adjusted models for clinical outcomes also adjusted for the demographic characteristics (race, ethnicity, and age) identified for the risk adjusted utilization models in order to maintain consistency across models.

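### The SAP analyses change in one survey scale, NPI-Q Distress, and leaves the protocol's other survey outcomes, including patient symptoms and caregiver depression, without an analysis or an explanation

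*SAP*

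**What the plan says.** **Protocol.** The secondary objective (Précis, Objectives) covers short-term effects on several constructs, among them "behavioral symptoms of dementia, caregiver burden, and caregiver depression". The measures table in section 6 places the NPI-Q under behavioral symptoms and the PHQ-8 under caregiver depression. It marks both, and the burden and strain scales, as primary and secondary outcomes; QOL-AD is marked secondary. Section 6.2.2 puts these instruments in a telephone survey at months three and nine, and 6.2.3 confirms that the baseline assessments are repeated at follow-up. Section 9.4 gives a general regression approach by outcome type, with random effects for nurses. Section 9.2 says the pilot should provide data for effect-size calculations for a full-scale study.

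**SAP.** Section 2.3 defines one secondary outcome: "The secondary outcome is the change in caregiver distress between baseline and 6-month follow-up survey". The instrument is "a brief proxy/caregiver-report of patient severity and caregiver distress across 12 neuropsychiatric symptom domains", and the scale used is the distress part ("Scores on the NPI-Q Distress scale can range from 0 to 60"). Section 7.2 lists the other scales for the Clinical Outcome Cohort as baseline characteristics: "NPI-Q Severity (patient symptom severity), PHQ-8 (caregiver depression), and Quick Dementia Rating Scale (patient dementia severity) from the baseline survey". Section 8.2 models change in Distress by difference-in-differences and uses baseline PHQ-8 for adjustment: "Models adjusted for differences in demographic characteristics (race, ethnicity, age) and PHQ-8 at baseline". The only other outcome analysed is utilization (2.2): "The primary outcome is the change in ED visits per member per month".

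**The concern.** The protocol built a survey around patient symptoms, caregiver depression, burden and quality of life, and the SAP carries forward one subscale. Two things are at stake.

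- **The secondary objective is only partly served.** SAP 2.1 keeps the aim of measuring short-term impact on both PWD and caregivers. Apart from ED visits, the one outcome analysed is the caregiver's reaction to symptoms. Nothing estimates whether the symptoms themselves, or caregiver depression, changed.
- **The pilot loses part of its product.** A later trial might reasonably take symptom severity or PHQ-8 as an endpoint. Following this SAP, its planners would have no estimate of effect or variability of change for either.

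There is also a reporting question. The SAP is written partly in the past tense, with achieved cohort sizes and observed baseline imbalances. When a document at that stage narrows a listed set of outcomes without a reason, readers will ask when and why the choice was made.

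**Working it through.** No figure in the plan is in dispute. The check compares where each survey construct appears.

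| Construct | Protocol objective (Précis) | Protocol section 6 table | Survey battery (6.2.2, repeated per 6.2.3) | Change analysed in SAP? |
|---|---|---|---|---|
| Behavioral symptoms | Named | NPI-Q, primary and secondary | NPI-Q | No. Severity at baseline only (7.2) |
| Caregiver distress | Not named | No row of its own | Noted as part of the NPI-Q | Yes (2.3, 8.2) |
| Caregiver depression | Named | PHQ-8, primary and secondary | PHQ-8 | No. Baseline descriptor (7.2) and covariate (8.2) |
| Caregiver burden or strain | Named | Zarit (survey) and Caregiver Strain Index (Epic), primary and secondary | Caregiver Strain Index | No |
| PWD quality of life | Not named | QOL-AD, secondary | QOL-AD | No |

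The one survey construct with an analysis has no row of its own in the protocol table. The three constructs that the objective names have no change analysis. The burden row also shows that the protocol table and battery name different survey instruments, so the SAP would need to say which one was given.

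**Side checks on the figures**

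- Distress range: 60 / 12 domains = 5 per domain, so the stated range is coherent.
- Planned completers of both surveys per arm (protocol 9.3): 150 × 0.5 × 0.5 = 37.5, which matches the stated 37.
- Achieved Distress cohort (SAP 7.1.2): 35 + 28 = 63 of the validated 143 + 113 = 256 (SAP 6), or 63 / 256 = 24.6%.

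**How precise would added estimates be?** As an illustration, assume the same 35 and 28 respondents for each scale, equal SDs and no clustering. The documents give no SD, so results are in units of the change-score SD.

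- Standard error = √(1/35 + 1/28) = 0.254 SD.
- 95% CI half-width = 1.96 × 0.254 = 0.50 SD.
- Difference detectable with 80% power at two-sided 0.05 = (1.96 + 0.84) × 0.254 = 0.71 SD.

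Clustering by nurse would widen these. The added estimates would be useful as pilot estimates with intervals, not as tests.

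**The case against.** **Distress is a legitimate outcome.** The protocol battery notes that the NPI-Q includes caregiver distress. The SAP labels the outcome as caregiver distress and hypothesises only a fall in distress. This stands. Distress may fall because symptoms ease or because the caregiver copes better, but that limits explanation of mechanism; it does not invalidate the outcome.

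**The protocol still covers the other scales.** It lists them as outcomes, section 9.4 gives a model that could be applied to them, and the SAP does not say they are withdrawn. This stands in part. A reader might infer that the trial cannot show whether symptoms or depression changed. The documents do not support that: the gap is in the SAP's specified analysis, while the design plans repeat measurement. But section 9.4 sets out no analysis outcome by outcome, and the SAP, which should do so, names a single secondary outcome.

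**Nothing shows selection on results.** A reader might infer that Distress was picked after the follow-up data were seen. The SAP discloses cohort sizes and baseline differences but no outcome result, so this is not shown. What is missing is a statement of timing and reason.

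**No depression effect was predicted here.** Protocol 2.2 says "Caregivers experienced decreased depression and caregiver burden within the first 6 months", but that describes the original navigator-delivered trial. It makes PHQ-8 worth estimating; it does not set an expectation for this adapted nurse training.

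**Follow-up data may be incomplete.** The SAP confirms completion at both waves only for Distress. The other scales were planned for follow-up, but their completeness is not documented. This stands and limits the fix to scales with follow-up data.

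**Conclusion.** The point holds as a mismatch between protocol and SAP. Among the survey outcomes the SAP analyses change only in NPI-Q Distress, and it gives no reason for omitting NPI-Q Severity, PHQ-8, burden or strain, and QOL-AD. All three constructs quoted from the protocol objective (symptoms, burden, depression) are left without an effect estimate.

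This does not invalidate the Distress analysis or the ED analysis. It means the SAP covers only part of its own secondary objective and yields fewer effect sizes than the pilot was meant to give. The conclusion rests on reading the SAP as the full list of planned analyses, and the remedy assumes the survey was repeated as the protocol planned.

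One further inference should be avoided even after the added scales are reported. A fall in Distress with no apparent change in Severity would not show caregiver adaptation. With 35 versus 28, a confidence interval of about ±0.50 SD is compatible with no change and with a moderate one.

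**What to change.** In SAP 2.3 and 8.2:

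1. Add between-group change in NPI-Q Severity and PHQ-8, and in burden or strain and QOL-AD where follow-up data exist. Name the burden instrument actually administered.
2. Label these exploratory. Report each as an estimate with a 95% CI beside Distress, and give the n per arm for each scale, since completers may differ.
3. Use a linear model with the nurse random effect of protocol 9.4, which SAP 8.2 does not mention. In the PHQ-8 model, enter baseline PHQ-8 only as the pre-measure. Copying the Distress model unchanged would use it twice.
4. State when and why Distress was chosen as the secondary outcome. For any protocol-listed survey outcome still left out, give the reason.
5. Present Distress and Severity side by side without a rule that reads mechanism from their combination.

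The cost is a few further models on data the protocol planned to collect, and some SAP text. The downside is more imprecise estimates to report from a small sample. With 63 respondents across 30 nurses (63 / 30 = 2.1 each), the nurse variance will also be poorly estimated, and the report should say so.
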